7. PATIENT ENROLLMENT

Before patients may be entered into the study, GW requires a copy of the relevant center's Ethics Committee (EC) or Institutional Review Board (IRB) written approval of the protocol, informed consent forms (ICFs) and other patient information material. Patients will be considered enrolled in the study from the time of providing written informed consent. All patients, or legal representatives, where appropriate, must personally sign and date the consent form prior to any procedures being performed (refer to [Section 9.1.2](#) and [Section 15.2](#)).

7.1 Treatment Assignment

At the start of Visit 1, patients will be allocated a unique patient number, consisting of a four digit GW center number and a three digit patient identification number. The three digit patient number will be assigned in ascendant numerical order at each site. The unique patient number will be preceded by a unique letter. For example, W1234001, denoting patient 001 at site 1234. GWP will provide all GWP42003-P/placebo packed and labelled. Following enrollment at Visit 2, patients will be allocated a pre-packed numbered IMP.

7.2 Randomization

This is a double-blind study. Patients will be randomized in a 4:1 ratio to receive 20 mg/kg GWP42003-P or placebo.

8. TREATMENT PROCEDURES

8.1 Investigational Medicinal Product Dosage, Administration and Schedule

The IMP will consist of three types of medication:

- GWP42003-P oral solution containing 100 mg/mL CBD.
- Placebo oral solution containing excipients.
- CLB (patient supplied).

The GWP42003-P/placebo will be presented as an oral solution containing either the active pharmaceutical ingredient and excipients (in the case of GWP42003-P) or only excipients (in the case of placebo). For details regarding GWP42003-P/placebo formulations, see [Section 5](#).

All patients will be weighed during the study visits and the daily volumes of GWP42003-P/placebo solution to be taken during the titration period, and for the remainder of the study, will be calculated and provided to the patient and/or caregiver. Further information on dispensing procedures will be provided in a separate Pharmacy Manual.

Each patient will take their first dose of GWP42003-P/placebo at Visit 2, Day 2 in the clinic. Patients not entering the OLE will take their final maintenance dose of GWP42003-P/placebo at Visit 4 (Day 33) in the clinic. Patients entering the OLE will take their final dose of IMP at Visit 11 (one year after the end of the blinded phase of the study) or sooner (if marketing authorization is granted within one year).

Patients will use their own supply of CLB throughout the study. Patients will continue on the dose that they were on at screening for the blinded phase of the study. CLB will only be an IMP for the blinded section of the study.

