4. EXPERIMENTAL PLAN

4.1 Study Design

This phase 2, placebo-controlled study consists of a 34 day, double-blind phase followed by an optional maximum one year OLE. Patients will continue to take CLB as advised by their physician for the duration of the study. GWP42003-P/placebo will be taken twice daily immediately after their CLB dose.

Patients will enter the study and begin a 10 day GWP42003-P or placebo titration phase. During this period patients will be up-titrated to a maintenance dose or equivalent of 20 mg/kg/day. Patients will continue to take this maintenance dose of GWP42003-P or placebo for 21 days (Days 12 to 32).

Upon completion of the treatment period (Day 34) patients will be invited to receive GWP42003-P during the OLE phase. If a patient enters the OLE they will take GWP42003-P as advised by the investigator. If a patient chooses not to enter the OLE, and/or the investigator does not feel it is in their best interests, they will taper off their GWP42003-P/placebo treatment by reducing their maintenance dose by 10% per day until dosing has ceased. For those patients not entering the OLE, dosing will end on Day 43 and they will receive a telephone follow-up visit four weeks after the end of GWP42003-P/placebo dosing (Day 71).

PK samples will be taken on two occasions during the blinded phase of the study:

- Day 1 (Visit 2) before beginning treatment (patients will be taking CLB only).
- Day 33 (Visit 4) following 21 days of GWP42003-P or placebo maintenance (patients will be taking CLB and GWP42003-P or placebo).

Ten samples will be taken during each PK assessment. PK samples should be taken at time points in respect to the morning dose of CLB. The time points are as follows: Pre-dose, 15 min, 30 min, 1 h, 1.5 h, 2 h, 4 h, 6 h, 12 h and 24 h. PK samples will be quantitatively analyzed for CLB, N-CLB, valproate (VPA), stiripentol (STP), levetiracetam (LEV) and topiramate (TPM) at Visit 2 and CLB, N-CLB, VPA, STP, LEV, TPM, CBD, CBD major metabolites, THC and THC major metabolites at Visit 4.

Patients should try to be consistent in the timing of their food intake in relation to dosing throughout the blinded phase of the study.

Upon entry into the OLE the dose of GWP42003-P and other AEDs may be adjusted up or down to a maximum of 30 mg/kg/day. The OLE will last for a maximum of one year or until marketing authorization is granted; whichever is earlier.

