8.1.2 Dose Escalation and Dose Adjustments

Patients will enter the blinded phase of the study and will be up-titrated over ten days (Day 2 to Day 11) to a maintenance dose or equivalent of GWP42003-P/placebo of 20 mg/kg/day. If GWP42003-P is not tolerated then the dose can be reduced accordingly at the discretion of the investigator. The titration regimen is described in [Table 8.1.2-1](#).

Table 8.1.2-1 Dose Up-titration Regimen*			
Day - GWP42003-P/Placebo (Blinded Period)	Dose Level (GWP42003-P or equivalent placebo)	Open label Extension** (GWP42003-P only) Day	Dose Level GWP42003-P
2	2.5 mg/kg	34	2.0 mg/kg
3	2.5 mg/kg	35	4.0 mg/kg
4	5.0 mg/kg	36	6.0 mg/kg
5	5.0 mg/kg	37	8.0 mg/kg
6	7.5 mg/kg	38	10.0 mg/kg
7	7.5 mg/kg	39	12.0 mg/kg
8	10.0 mg/kg	40	14.0 mg/kg
9	10.0 mg/kg	41	16.0 mg/kg
10	15.0 mg/kg	42	18.0 mg/kg
11	15.0 mg/kg	43	20.0 mg/kg
12 onwards	20.0 mg/kg	44	20.0 mg/kg***

* GWP42003-P /placebo is to be taken twice daily. Total daily doses are shown.

** Only patients who were taking placebo during the double-blind period will up-titrate according to this schedule during the OLE period. Those taking GWP42003-P during the double-blind period will down-titrate their blinded IMP whilst simultaneously up-titrating with GWP42003-P, thus maintaining a daily dose of 20 mg/kg/day GWP42003-P throughout.

*** The GWP42003-P dose of 20 mg/kg/day can be adjusted during the OLE period, after Visit 5, at the investigator's discretion: up to a maximum dose of 30 mg/kg/day. It may also be adjusted down (no minimum).

The titration regimen defined above should be followed to the maximum dose (20 mg/kg/day). Should an AE occur during titration which is attributable to IMP or concomitant AED, then IMP dose should be reduced to the next lower dose. Any other changes in concomitant AED therapy should be reviewed with the medical monitor before being initiated.

For those patients who do not enter the OLE the dose of GWP42003-P/placebo will taper off over 10 days beginning on Day 34. The patient will reduce the dose by 10% of the maintenance dose each day and treatment will end on Day 43.

Patients who enter the OLE period will be transitioned to the OLE treatment over a 10-day period in order to maintain blinding, simultaneously down-titrating blinded GWP42003-P /placebo whilst up-titrating open-label GWP42003-P. As such, patients

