who were taking GWP42003-P during the blinded period will maintain their 20 mg/kg/day dose throughout the transition from the blinded period into the OLE period and patients who received placebo during the blinded period up-titrate slowly to the 20 mg/kg/day dose in the OLE period. After this has taken place after Visit 5, the maintenance dose of GWP42003-P may be adjusted up or down at the discretion of the investigator to a maximum of 30 mg/kg/day (no minimum).

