9.1.14 Investigational Medicinal Product Accountability

GWP42003-P/placebo will be dispensed at each of the following visits during the blinded phase:

- Visit 2 (Day 2)
- Visit 4 (Day 34)

IMP will be dispensed at each of the following visits for patients entering the OLE:

- Visit 5 (Two weeks)
- Visit 6 (One month)
- Visit 7 (Two months)
- Visit 8 (Three months)
- Visit 9 (Six months)
- Visit 10 (Nine months)
- Visit 11 (12 months)

Patients will be asked to return all IMP (used and unused) to each relevant visit (Visits 2 to 12). The site will check the returned IMP against the usage recorded in the paper diary. Any discrepancies will be discussed with the patient/caregiver and documented accordingly within the patient's source documents.

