9.2.1.3 Visit 3 (Day 12 +3 days)

This visit will occur 11 days after Visit 2, Day 1 (enrollment). Patients will return all used and unused GWP42003-P/placebo. The following observations will be made at Visit 3 (Day 12): concomitant medications (including AEDs), physical examination (including body weight), ECG, vital signs, AEs and review of patient diary completion.

Clinical laboratory samples (blood and urine) will be taken for hematology, biochemistry and urinalysis. The C-SSRS will be administered.

9.2.1.4 Visit 4

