9.2.1.4.2 Visit 4 (Day 34)

This is the second part of the two day visit. The final PK sample will be collected 24 hours after the Day 33 morning CLB dose.

Following completion of the PK sampling process the following observations will be made on Day 34: concomitant medications (including AEDs), physical examination (including body weight), vital signs and AEs.

At the end of the blinded phase of the study on Day 34, providing the investigator and patient both agree, patients will be invited to continue taking GWP42003-P and to enter the OLE.

Patients who enter the OLE will be dispensed GWP42003-P on Day 34 and the first dose will be taken in clinic. Following administration of GWP42003-P, patients must remain in clinic for at least 30 minutes to monitor for any adverse reactions. At the point of entry to the OLE, patients will be transitioned to the OLE treatment over a 10 day period in order to maintain blinding.

Patients who do not enter the OLE will begin a 10 day taper period during which they will taper off their daily dose of GWP42003-P/placebo. The daily dose will be reduced by 10% of the maintenance dose per day and treatment will end on Day 42.

9.2.1.5 Visit 5 (Patients not entering Open Label Extension) (Day 43 + 3 days)

This visit will occur 42 days after Visit 2, Day 1 (enrollment) for those patients who do not enter the OLE.

All GWP42003-P/placebo (used and unused) will be collected and a check of the returned GWP42003-P/placebo against usage must be made. A physical examination (including body weight), ECG and vital signs will be assessed and the C-SSRS will be administered. The trained investigator or study coordinator will complete the Study Medication Use and Behavior Survey as an interview with the patient/caregiver. Clinical laboratory samples (blood and urine) will be taken for hematology, biochemistry and urinalysis and a review of concomitant medications (including AEDs) and AEs will be completed. Patient diaries will be collected.

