9.2.2.6 Visit 10 (Open Label Extension) - Nine Months (\pm 7 days)

This visit will occur nine months after Visit 4 (Day 34). Patients will return all used and unused IMP. The following observations will be made at Visit 10 (OLE): concomitant medications (including AEDs), physical examination (including body weight), ECG, vital signs, review of seizure diary and AEs.

Clinical laboratory samples (blood and urine) will be taken for hematology, biochemistry and urinalysis. The C-SSRS will be administered. The investigator must record the patient's attendance at the visit and the outcome.

The investigator must assess adherence to the dosing regimen and recording of rescue medications by reviewing the patient's diary.

9.2.2.7 Visit 11 (Open Label Extension End of Treatment) - Twelve Months (\pm 7 days)

This visit will occur twelve months after Visit 4 (Day 34). Patients will return all used and unused IMP. The following observations will be made at Visit 11 (OLE): concomitant medications (including AEDs), physical examination (including body weight), ECG, vital signs, review of seizure diary and AEs.

Clinical laboratory samples (blood and urine) will be taken for hematology, biochemistry and urinalysis. The C-SSRS will be administered. The investigator must record the patient's attendance at the visit and the outcome.

The investigator must assess adherence to the dosing regimen and recording of rescue medications by reviewing the patient's diary.

Starting at Visit 11, patients will begin to taper down their IMP dose. The dose will be reduced by 10% of their OLE maintenance dose per day.

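### Sections 8.1 and 4.1 contradict the sections on dose adjustment and visits about when open-label dosing ends and when the dose may first be changed

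*Protocol*

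**What the plan says.** All references are to Version 4 of the protocol.

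- **End of OLE dosing.** Section 8.1: "Patients entering the OLE will take their final dose of IMP at Visit 11", or sooner if marketing authorization is granted. Section 9.2.2.7: "Starting at Visit 11, patients will begin to taper down their IMP dose", in daily steps of 10% of the OLE maintenance dose. Section 9.2.2.8 puts the end-of-taper visit (Visit 12) ten days after Visit 11. Section 9.1.14 and Appendix 1 list Visit 11 as a dispensing visit.
- **First permitted dose change in the OLE.** Section 4.1: "Upon entry into the OLE the dose of GWP42003-P and other AEDs may be adjusted up or down to a maximum of 30 mg/kg/day". Section 8.1.2, following its description of the 10-day transition: "After this has taken place after Visit 5, the maintenance dose of GWP42003-P may be adjusted up or down". The footnote to Table 8.1.2-1 also says after Visit 5, and Section 9.2.2.1 places the adjustment at Visit 5.
- **End of taper for patients not entering the OLE.** Section 9.2.1.4.2 and the synopsis text for Day 34: "treatment will end on Day 42". Section 8.1.2: "treatment will end on Day 43"; Section 4.1 also has dosing end on Day 43.
- **Supply during the blinded phase.** Section 9.2.1.3, at Visit 3 (Day 12): "Patients will return all used and unused GWP42003-P/placebo". Section 9.2.1.4.1 requires the same on Day 33. Section 9.1.14 introduces its list with "GWP42003-P/placebo will be dispensed at each of the following visits during the blinded phase" and names only Day 2 and Day 34; Appendix 1 agrees. Section 9.2.1.2.2 describes the Day 2 issue as serving the titration and maintenance periods.

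**The concern.** Sites act on these passages, and on the first two points a site that follows one passage breaks another.

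At Visit 11, one reading stops the drug that day and the other begins a stepwise reduction with newly dispensed IMP, in patients with epilepsy. At OLE entry, Section 4.1 lets the investigator change the dose on Day 34. On that day patients are only starting a double-blind cross-titration, and former placebo patients are on its first step. Section 4.1 also, as worded, attaches a mg/kg/day ceiling to the other AEDs as well as to GWP42003-P.

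The other two points are smaller: a one-day difference in the end of the taper, and silence on what happens to the bottles collected on Day 12 and Day 33 while dosing goes on.

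**Working it through.** The plan gives no statistical figure to reproduce here. The check compares the passages and counts days.

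**1. Last OLE dose.** Inputs: taper starts at Visit 11 in steps of 10% of the maintenance dose per day (9.2.2.7); Visit 12 is ten days later (9.2.2.8). Let k be the number of days after Visit 11.

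- If Visit 11 is already the first reduced day, dose = 90% − 10% × k. This gives 10% at k = 8 and 0% at k = 9, so the last non-zero dose is 8 days after Visit 11.
- If Visit 11 is still at full dose, dose = 100% − 10% × k. This gives 10% at k = 9 and 0% at k = 10, so the last non-zero dose is 9 days after.

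Neither reading puts the final dose at Visit 11, as Section 8.1 does. The ten days in 9.2.2.8 are the interval to Visit 12, not to the last dose.

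**2. First dose change in the OLE.** Inputs: OLE entry is Day 34; Visit 5 is two weeks later, ± 3 days (9.2.2.1); the transition runs over Days 34 to 43 (Table 8.1.2-1).

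- Visit 5 = 34 + 14 = Day 48, window Day 45 to Day 51.
- Gap between the two rules = 48 − 34 = 14 days (range 11 to 17).
- Even the earliest Visit 5 (Day 45) comes after the transition ends (Day 43), so the gap contains all ten transition days.
- Table 8.1.2-1 has former placebo patients at 2.0 mg/kg on Day 34, reaching 20.0 mg/kg on Day 43. With 20 patients randomized 4:1 they number 20 × 1/5 = 4, if all of them enter the optional OLE. The conflicting rule itself applies to every entrant.

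**3. Taper outside the OLE.** Inputs: taper begins on Day 34 in steps of 10% of the maintenance dose (8.1.2).

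| First taper day (Day 34) | Day 42 | Day 43 | Day 44 |
|---|---|---|---|
| 90% | 10% | 0% | – |
| 100% | 20% | 10% | 0% |

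The last non-zero dose is Day 42 on the first line and Day 43 on the second, a difference of one day. Section 4.1 sets the follow-up call four weeks after the end of dosing at Day 71; 43 + 28 = 71 and 42 + 28 = 70, and both lie inside the ± 3 day window.

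**4. Blinded-phase supply.** Dosing days from the Day 12 collection to Day 33 inclusive = 33 − 12 + 1 = 22, with no dispensing listed in between. The Day 2 issue is described as 10 + 21 = 31 days, that is Days 2 to 32. Day 33 is a further dosing day: all IMP is collected at that visit, an evening dose is required after the 12-hour sample (9.2.1.4.1), and the next listed dispensing is Day 34. In the OLE schedule, Visits 5 to 11 each show collection together with dispensing; Visit 3 shows collection alone.

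**The case against.** The strongest reply is that these are drafting slips which the operational text already corrects.

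- **Visit 11.** The sentence in Section 8.1 just before the disputed one speaks of the final maintenance dose for patients not entering the OLE, so the OLE sentence may simply have lost that qualifier. The visit text describes only the taper, and the Definition of Terms and Section 9.1.16 treat Visit 12 as the end of treatment or final dosing visit for these patients. This is a plausible origin for the error, but Section 8.1 is the dosing section and as written it says something else. A reader might go further and infer that the AE follow-up period moves with the choice. Section 12.1.1 does count 28 days from the last dose, but Section 9.2.2.9 schedules the call from the end of taper, and Sections 12.3 and 12.6 run AE recording to Visit 13. That consequence is weak.
- **OLE adjustment.** Section 4.1 is an overview and refers readers to Sections 8 and 9 for detail. The synopsis is not in conflict: its design text gives no timing and its Visit 5 entry matches 9.2.2.1. The wording about other AEDs is probably a matter of grammar, since Section 3.3.1 ties the maximum to GWP42003-P alone. All of this limits the damage, but Section 4.1 still grants a permission on Day 34 that Section 8.1.2 withholds.
- **Day 42 or Day 43.** Visit 5 stays on Day 43 and the call on Day 71 either way, so no assessment moves.
- **Day 12 supply.** A reader might infer that patients have no study drug on Days 12 to 33 and that the primary PK question then cannot be answered. The documents do not support that. Section 9.2.1.2.2 has the Day 2 supply serve titration and maintenance, Sections 8.4 and 9.1.14 make the return a check against the diary, Section 5.3.1 promises sufficient IMP at each dispensing, and Section 8.1 leaves dispensing detail to a Pharmacy Manual that is not at hand. Nothing says that the bottles are withheld. What remains is that nothing says they are handed back either.

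**Conclusion.** The point holds for two direct contradictions in operative dosing text. Section 8.1 ends OLE dosing at Visit 11, while the taper passages put the last non-zero dose 8 or 9 days later, depending on whether Visit 11 is a reduced or a full-dose day. Section 4.1 opens dose adjustment about 14 days (11 to 17) before Section 8.1.2 does, a span that covers the whole blinded transition. It concerns every patient entering the OLE, most of all up to 4 former placebo patients at the first step.

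The Day 42/43 difference is real but minor. The collection at Visit 3 and on Day 33 is a minor gap in wording, with no demonstrated interruption of dosing and no demonstrated threat to the primary PK comparison. The day counts assume the scheduled visit days and a taper in equal 10% steps.

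**What to change.** Issue one consistency amendment so that each rule is stated once or identically wherever it appears:

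- reconcile Section 8.1 with 9.2.2.7, 9.2.2.8, 9.1.14 and Appendix 1 on how OLE dosing ends;
- reconcile Section 4.1 with 8.1.2 and 9.2.2.1 on when the OLE dose may change, and reword 4.1 so that it is clear which drug the maximum refers to;
- reconcile Day 42 (9.2.1.4.2 and synopsis) with Day 43 (4.1 and 8.1.2), stating which day is the first reduced dose;
- reconcile the Visit 3 and Day 33 collections (9.2.1.3, 9.2.1.4.1) with 9.1.14 and Appendix 1, stating how dosing continues after each collection.

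Which clinical rule stands in each case is for the sponsor's physicians. The cost is the amendment itself; no procedure, visit or sample is added.

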8.1.1 Dose Administration

GWP42003-P/placebo will be administered orally by the patient or their caregiver twice each day (morning and evening) using the syringe(s) provided.

GWP42003 P/placebo should be taken immediately after the patient's usual CLB administration. The GWP42003-P/placebo should be swallowed, as per the intended commercial therapeutic route, and may be taken with other concomitant medications, as directed by the investigator.

8.1.2 Dose Escalation and Dose Adjustments

Patients will enter the blinded phase of the study and will be up-titrated over ten days (Day 2 to Day 11) to a maintenance dose or equivalent of GWP42003-P/placebo of 20 mg/kg/day. If GWP42003-P is not tolerated then the dose can be reduced accordingly at the discretion of the investigator. The titration regimen is described in [Table 8.1.2-1](#).

Table 8.1.2-1 Dose Up-titration Regimen*			
Day - GWP42003-P/Placebo (Blinded Period)	Dose Level (GWP42003-P or equivalent placebo)	Open label Extension** (GWP42003-P only) Day	Dose Level GWP42003-P
2	2.5 mg/kg	34	2.0 mg/kg
3	2.5 mg/kg	35	4.0 mg/kg
4	5.0 mg/kg	36	6.0 mg/kg
5	5.0 mg/kg	37	8.0 mg/kg
6	7.5 mg/kg	38	10.0 mg/kg
7	7.5 mg/kg	39	12.0 mg/kg
8	10.0 mg/kg	40	14.0 mg/kg
9	10.0 mg/kg	41	16.0 mg/kg
10	15.0 mg/kg	42	18.0 mg/kg
11	15.0 mg/kg	43	20.0 mg/kg
12 onwards	20.0 mg/kg	44	20.0 mg/kg***

* GWP42003-P /placebo is to be taken twice daily. Total daily doses are shown.

** Only patients who were taking placebo during the double-blind period will up-titrate according to this schedule during the OLE period. Those taking GWP42003-P during the double-blind period will down-titrate their blinded IMP whilst simultaneously up-titrating with GWP42003-P, thus maintaining a daily dose of 20 mg/kg/day GWP42003-P throughout.

*** The GWP42003-P dose of 20 mg/kg/day can be adjusted during the OLE period, after Visit 5, at the investigator's discretion: up to a maximum dose of 30 mg/kg/day. It may also be adjusted down (no minimum).

The titration regimen defined above should be followed to the maximum dose (20 mg/kg/day). Should an AE occur during titration which is attributable to IMP or concomitant AED, then IMP dose should be reduced to the next lower dose. Any other changes in concomitant AED therapy should be reviewed with the medical monitor before being initiated.

For those patients who do not enter the OLE the dose of GWP42003-P/placebo will taper off over 10 days beginning on Day 34. The patient will reduce the dose by 10% of the maintenance dose each day and treatment will end on Day 43.

Patients who enter the OLE period will be transitioned to the OLE treatment over a 10-day period in order to maintain blinding, simultaneously down-titrating blinded GWP42003-P /placebo whilst up-titrating open-label GWP42003-P. As such, patients

who were taking GWP42003-P during the blinded period will maintain their 20 mg/kg/day dose throughout the transition from the blinded period into the OLE period and patients who received placebo during the blinded period up-titrate slowly to the 20 mg/kg/day dose in the OLE period. After this has taken place after Visit 5, the maintenance dose of GWP42003-P may be adjusted up or down at the discretion of the investigator to a maximum of 30 mg/kg/day (no minimum).

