8.2 Concomitant Therapy

Doses of any concomitant AEDs, including CLB, must have been stable for at least four weeks prior to screening and must remain stable throughout the blinded phase of the study. If there are symptoms of toxicity suspected to be from a drug interaction, the investigator may adjust GWP42003-P/placebo or the CLB or other AEDs after discussion with the medical monitor.

The use of rescue medication is allowed if necessary. The use of oxygen may be considered as rescue medication if used as required. Any medication, other than the IMP, taken during the study must be recorded on the Case Report Form (CRF).

Any non-pharmacological therapies (e.g., ketogenic diet, VNS) must also be stable up to four weeks prior to baseline and throughout the duration of the study.

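### The blinded dose may be reduced, but the OLE transition text holds every active-arm patient at 20 mg/kg/day, and Sections 4.1 and 8.1.2 disagree on when OLE adjustment may start

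*Protocol*

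**What the plan says.** **Reduction in the blinded phase.** Section 8.1.2 provides: "If GWP42003-P is not tolerated then the dose can be reduced accordingly at the discretion of the investigator". No lower limit is given. For an adverse event during titration attributable to IMP or a concomitant AED, "then IMP dose should be reduced to the next lower dose". Section 8.2 adds a second route: if toxicity from a drug interaction is suspected, "the investigator may adjust GWP42003-P/placebo or the CLB or other AEDs after discussion with the medical monitor".

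**Transition into the OLE.** Section 8.1.2 says: "Patients who enter the OLE period will be transitioned to the OLE treatment over a 10-day period in order to maintain blinding". Blinded product goes down while open-label product goes up. For patients on active drug, the second footnote to Table 8.1.2-1 describes the result as "thus maintaining a daily dose of 20 mg/kg/day GWP42003-P throughout", and the body text says that they "will maintain their 20 mg/kg/day dose throughout the transition from the blinded period into the OLE period". Neither makes an exception. Section 9.2.2.1 (OLE Visit 5), like the synopsis, starts any later adjustment from a 20 mg/kg/day dose reached when the 10-day transition ends.

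**When the OLE dose may be changed.** The third footnote to Table 8.1.2-1 says that the 20 mg/kg/day dose "can be adjusted during the OLE period, after Visit 5, at the investigator's discretion"; the body of 8.1.2 agrees. Section 4.1 says: "Upon entry into the OLE the dose of GWP42003-P and other AEDs may be adjusted up or down to a maximum of 30 mg/kg/day".

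**The concern.** The two parts of Section 8.1.2 cannot both hold for a patient who finishes the blinded phase on less than 20 mg/kg/day. Such a patient has no 20 mg/kg/day dose to maintain, and following the transition text means raising the dose. The clause on later adjustment does not settle the matter, because Sections 4.1 and 8.1.2 give different starting times.

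The case is foreseeable. The clinical hypothesis in Section 3.4 is that GWP42003-P may alter CLB and N-CLB exposure, and Section 8.2 plans for toxicity from such an interaction. The transition is also run so as to keep the blind, so a site need not know which of its dose-reduced patients are on active drug. At stake is an unintended return to a dose that was reduced for tolerability, with early OLE adverse events in those patients confounded with re-escalation. With 20 patients randomized 4:1, about 20 × 4/5 = 16 are on active drug. Only those who are dose-reduced and also enter the OLE are concerned.

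**Working it through.** **Inputs**
- Open-label steps: 2, 4, …, 20 mg/kg on Days 34 to 43, from the OLE column of Table 8.1.2-1. The footnote assigns this schedule to former placebo patients. I assume that active patients take the same open-label steps, as keeping the blind requires.
- Blinded down-titration for OLE entrants: not stated. Section 8.1.2 gives 10% of the maintenance dose per day, but only for patients who do not enter the OLE. I therefore show alternatives.
- Reduced blinded dose m: 15, 10, 7.5 and 5 mg/kg/day. These are levels from the protocol's own titration table and are illustrative; the protocol does not predict how many patients would be reduced or how far.
- OLE Visit 5: two weeks after Day 34, so Day 34 + 14 = Day 48, with a ± 3 day window of Day 45 to 51.

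**Reproducing the protocol's figure.** On transition day i (i = 1 to 10, that is Day 33 + i), with a 10% taper, the total is m(1 − 0.1i) + 2i. For m = 20 this is 20 − 2i + 2i = 20 on each of Days 34 to 43. The stated 20 mg/kg/day reproduces.

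**Reduced doses, three readings**
1. *Literal text.* The total is 20 mg/kg/day from Day 34, so the ratio to the reduced dose is 20/m.
2. *Taper of 10% of the patient's own dose.* Total minus m = i(2 − 0.1m) = 0.1i(20 − m), which is positive for every m below 20. On Day 34 the total is 0.9m + 2.
3. *Fixed 2 mg/kg blinded steps down to zero.* The total is max(0, m − 2i) + 2i. It stays at m until the blinded product runs out and then follows the open-label column.

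| m (mg/kg/day) | 20/m | Reading 2: Day 34 total | Reading 2: first day above m | Reading 3: first day above m | Day 43 total, all readings |
|---|---|---|---|---|---|
| 15 | 1.33 | 15.5 | 34 | 41 | 20 |
| 10 | 2.00 | 11.0 | 34 | 39 | 20 |
| 7.5 | 2.67 | 8.75 | 34 | 37 | 20 |
| 5 | 4.00 | 6.5 | 34 | 36 | 20 |

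All three readings end at 20 mg/kg/day on Day 43. That is 5 days before the nominal Visit 5 (48 − 43), or 2 to 8 days allowing for the window (45 − 43 to 51 − 43).

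**The case against.** A reader might infer that downward adjustment is barred until Visit 5. The documents do not support that.
- The adverse-event step-down sentence stands directly below a table that holds both the blinded and the OLE columns, and it can be read as covering Days 34 to 43.
- The Section 8.2 route for suspected interaction toxicity is open, and Section 4.1 has OLE patients dosed on the investigator's advice.
- The rationale in amendment 2 for the Visit 5 timing speaks of further increases, not of reductions.
- Entry to the OLE is optional and needs the agreement of investigator and patient.

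All of this stands and softens the consequence. It does not resolve the conflict. The step-down acts only after an adverse event, and the other routes are discretionary. None says what a dose-reduced patient takes on Days 34 to 43, and the current text of 8.1.2 defers adjustment in both directions until after Visit 5.

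Two other strong readings also fail. One is that the reduced dose is necessarily exceeded from Day 34; under fixed 2 mg/kg steps this happens on Day 36 to 41 for the doses shown. The other is that early OLE adverse events become uninterpretable. IMP intake is recorded daily (Section 9.1.13) and each adverse event carries causality and action taken (Section 12.6), so the daily dose can be reconstructed after unblinding.

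**Conclusion.** The point holds as an internal contradiction with a safety consequence. The protocol allows reduced blinded doses, describes a transition that is correct only for a patient at 20 mg/kg/day, and gives two different times from which the OLE dose may be changed. Followed as written, it takes a dose-reduced OLE entrant to 20 mg/kg/day by Day 43, before Visit 5. For one level down (15 mg/kg/day) the end ratio is 1.33; it reaches 4 at 5 mg/kg/day.

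The end ratios depend on the illustrative reduced dose but not on the taper. The day of first excess rests on the assumed taper and on active patients taking the tabulated open-label steps. The number of patients affected cannot be derived from the protocol. The Day 33 PK comparison precedes the transition and is untouched.

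**What to change.** Reconcile Section 4.1, Section 8.1.2 with the footnotes to Table 8.1.2-1, Section 8.2, Section 9.2.2.1 and the matching OLE Visit 5 text in the synopsis. The reconciled text should:
- say how the transition applies to patients whose blinded dose was reduced, including the blinded down-titration steps for OLE entrants;
- give one time from which OLE adjustment is allowed;
- say whether the adverse-event step-down applies during the transition.

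The sponsor's medical team decides the rule; none is proposed here. The cost is protocol wording and a line in the individual dosing schedules. No analysis or sample size changes.
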